## CONFIDENTIAL

201190 (ZOSTER-049 EXT:006-022)  
Statistical Analysis Plan Amendment 3

Sub-group order in tables	Sub-group label in tables	Sub-group definition for footnote
Age Group – Age strata 1 (for efficacy in LTFU and Control group)		
1	50-59 YOA	50-59 YOA at primary vaccination
2	60-69 YOA	60-69 YOA at primary vaccination
3	70-79 YOA	70-79 YOA at primary vaccination
4	≥ 80 YOA	≥ 80 YOA at primary vaccination
5	≥ 60 YOA	≥ 60 YOA at primary vaccination
6	≥ 70 YOA	≥ 70 YOA at primary vaccination
Age Group – Age strata 2 (only for immunogenicity and safety analysis in LTFU group)		
1	50-59 YOA	50-59 YOA at primary vaccination
2	60-69 YOA	60-69 YOA at primary vaccination
3	≥70 YOA	≥70 YOA at primary vaccination
4	≥60 YOA*	≥60 YOA at primary vaccination
Gender		
1	Female	Female
2	Male	Male
Ethnicity		
1	American Hispanic or Latino	American Hispanic or Latino
2	Not American Hispanic or Latino	Not American Hispanic or Latino
Race		
1	African Heritage/African American	African Heritage/African American
2	Asian	Asian-Central/South Asian Heritage, Asian-East Asian Heritage, Asian- Japanese Heritage and Asian – South East Asian Heritage
3	White	White – Arabic/North African heritage and White – Caucasian / European Heritage
4	Other	American Indian or Alaskan Native, Native Hawaiian or Other Pacific Islander and other

Sub-group order in tables	Sub-group label in tables	Sub-group definition for footnote
Region		
1	North America	Canada, United States
2	Australasia	Australia, Hong Kong, Japan, Korea Republic of, Taiwan
3	Europe	Czechia, Estonia, Finland, France, Germany, Italy, Spain, Sweden, United Kingdom
4	Latin America	Brazil, Mexico

\* Age stratum  $\geq 60$  YOA is not used for safety analysis in LTFU

### 3. OBJECTIVES

The statistical analyses to be performed for the study objectives described in Sections 3.1 and 3.2 will be descriptive. No success criteria have been defined.

#### 3.1. Primary objective

- To assess the VE in the prevention of HZ over the total duration of the ZOSTER-049 study as measured by the reduction in HZ risk in subjects  $\geq 50$  YOA overall at the time of first vaccination in the ZOSTER-006/022 studies.

Refer to Section 4.1 for the definition of the primary endpoint.

[figure not shown]
#### 3.2. Secondary objectives

- To assess the VE in the prevention of HZ over the total duration of the ZOSTER-049 study as measured by the reduction in HZ risk in subjects within each of the age ranges\* at the time of first vaccination in the ZOSTER-006/022 studies;
- To assess the VE in the prevention of HZ from one month post dose 2 in the ZOSTER-006/022 studies until the end of the ZOSTER-049 study as measured by the reduction in HZ risk in subjects  $\geq 50$  YOA overall and within each of the specified age ranges\* at the time of first vaccination in the ZOSTER-006/022 studies;
- To assess the VE in the prevention of HZ over each year of follow-up from one month post dose 2 in the ZOSTER-006/022 studies as measured by the reduction in HZ risk in subjects  $\geq 50$  YOA overall and within each of the specified age ranges\* at the time of first vaccination in the ZOSTER-006/022 studies;
- To assess the VE over the total duration of the ZOSTER-049 study in prevention of PHN in subjects  $\geq 50$  YOA overall and within each of the specified age ranges\* at the time of first vaccination in the ZOSTER-006/022 studies;

- To assess the VE in the prevention of PHN from one month post dose 2 in the ZOSTER-006/022 studies until the end of the ZOSTER-049 study in subjects  $\geq 50$  YOA and within each of the specified age ranges\* at the time of first vaccination in the ZOSTER-006/022 studies;
- To assess the VE over the total duration of the ZOSTER-049 study in prevention of HZ related complications (other than PHN) in subjects  $\geq 50$  YOA overall and within each of the specified age ranges\* at the time of first vaccination in the ZOSTER-006/022 studies;
- To assess the VE in the prevention of HZ related complications (other than PHN) from one month post dose 2 in the ZOSTER-006/022 studies until the end of the ZOSTER-049 study in subjects  $\geq 50$  YOA overall and within each of the specified age ranges\* at the time of first vaccination in the ZOSTER-006/022 studies;
- To assess persistence of humoral immune responses at Year 5, 6, 7, 8, 9 and 10 and beyond after the primary vaccination in the ZOSTER-006/022 studies in the HI subset in subjects  $\geq 50$  YOA overall and within each of the specified age ranges\* at the time of first vaccination, in the ZOSTER-006/022 studies;
- To assess persistence of vaccine induced cell-mediated immune responses at Year 5, 6, 7, 8, 9 and 10 and beyond after the primary vaccination in the ZOSTER-006/022 studies **in the CMI subset** in subjects  $\geq 50$  YOA overall and within each of the specified age ranges\* at the time of first vaccination, in the ZOSTER-006 study;
- To assess humoral immune responses at Year 5, 6, 7, 8, 9 and 10 and beyond after the primary vaccination in the ZOSTER-006/022 studies in subjects  $\geq 50$  YOA at the time of first vaccination, in the ZOSTER-006/022 studies, who had a confirmed HZ episode previously for the timepoint considered;
- To assess vaccine induced cell-mediated immune responses at Year 5, 6, 7, 8, 9 and 10 and beyond after the primary vaccination in the ZOSTER-006/022 studies **in the CMI subset** in subjects  $\geq 50$  YOA at the time of first vaccination, in the ZOSTER-006 study, who had a confirmed HZ episode previously for the timepoint considered;
- To assess humoral immune responses one month after the first additional HZ/su vaccine dose (1-Additional Dose and Revaccination groups) and at the same timepoint in the Control group;
- To assess vaccine induced cell-mediated immune responses one month after the first additional HZ/su vaccine dose (1-Additional Dose and Revaccination groups) and at the same timepoint in the Control group;
- To assess humoral immune responses one month after the second additional HZ/su vaccine doses (Revaccination group and at the same timepoint in the Control group);
- To assess vaccine induced cell-mediated immune responses one month after the second additional HZ/su vaccine doses (Revaccination group and at the same timepoint in the Control group);
- To assess persistence of humoral immune responses at Year 1, 2, 3, 4, 5 and 6 timepoints of this study in subjects from the 1-Additional Dose, Revaccination and Control groups;

- To assess persistence of vaccine induced cell-mediated immune responses at Year 1, 2, 3, 4, 5 and 6 timepoints of this study in subjects from the 1-Additional Dose, Revaccination and Control groups;
- To assess vaccine safety and reactogenicity in the 1-Additional Dose and Revaccination groups;
- To assess vaccine safety in the LTFU and Control groups.

### **3.3. Tertiary objectives (Amended 23 September 2019)**

## **4. ENDPOINTS**

### **4.1. Primary endpoint**

- Confirmed HZ cases (LTFU and Control groups);
  - Confirmed HZ cases during the ZOSTER-049 study.

### **4.2. Secondary endpoints**

- Confirmed HZ cases;
  - Confirmed HZ cases since one month post dose 2 in the previous ZOSTER-006/022 studies;
- PHN cases;
  - PHN cases during the ZOSTER-049 study and since one month post dose 2 in the previous ZOSTER-006/022 studies;

- HZ related complications (other than PHN);
  - HZ related complications (other than PHN) during the ZOSTER-049 study and since one month post dose 2 in the previous ZOSTER-006/022 studies;
- Anti-gE humoral immunogenicity at Months 0, 12, 24, 36, 48, 60 and 72 (LTFU HI subset, 1-Additional Dose, Revaccination and Control groups), at Month 1 (1-Additional Dose, Revaccination and Control groups), and at Month 3 (Revaccination and Control groups);
  - Anti-gE Ab concentrations as determined by ELISA;
- CMI in terms of frequencies of antigen-specific CD4+ T cells at Months 0, 12, 24, 36, 48, 60 and 72 (LTFU CMI subset, 1-Additional Dose, Revaccination and Control groups), at Month 1 (1-Additional Dose, Revaccination and Control groups), and at Month 3 (Revaccination and Control groups);
  - Frequencies of CD4+ T cells with antigen-specific Interferon gamma (IFN- $\gamma$ ) and/or Interleukin-2 (IL-2) and/or Tumour Necrosis Factor alpha (TNF- $\alpha$ ) and/or CD40 Ligand (CD40L) secretion/expression to gE as determined by ICS;
- Solicited local and general symptoms in subjects administered with 1 or 2 additional doses of HZ/su vaccine (1-Additional Dose and Revaccination groups);
  - Occurrence, intensity and duration of each solicited local symptom within 7 days (Days 0 - 6) after each vaccination;
  - Occurrence, intensity, duration and relationship to vaccination of each solicited general symptom within 7 days (Days 0 - 6) after each vaccination;
- Unsolicited AEs in subjects administered with 1 or 2 additional doses of HZ/su vaccine (1-Additional Dose and Revaccination groups);
  - Occurrence, intensity and relationship to vaccination of unsolicited AEs during 30 days (Days 0 - 29) after each vaccination, according to the Medical Dictionary for Regulatory Activities (MedDRA) classification;
- Serious AEs;
  - Occurrence and relationship to vaccination of all SAEs;
    - from Visit Month 0 until 12 months: for Control and 1-Additional Dose groups;
    - from Visit Month 0 until 12 months after last HZ/su vaccination: for the Revaccination group;
  - Occurrence of SAEs related to investigational vaccine, related to study participation or to GSK concomitant medication/vaccine during the entire study period in all subjects;

- Occurrence of AEs of specific interest: Potential immune-mediated diseases (pIMDs) (1-Additional Dose, Revaccination and Control groups);
  - Occurrence and relationship to vaccination of all pIMDs;
    - from Visit Month 0 until 12 months: for Control and 1-Additional Dose groups;
    - from Visit Month 0 until 12 months after last HZ/su vaccination: for the Revaccination group.

#### **4.3. Tertiary endpoints**

CCI

### **5. STUDY POPULATION**

#### **5.1. Total Vaccinated cohort**

The Total Vaccinated cohort (TVC) will include all subjects from the ZOSTER-006/022 studies who are enrolled in the ZOSTER-049.

The TVC for efficacy will include all subjects in the LTFU and control groups for whom data related to efficacy endpoints are available.

The TVC for the groups 1-Additional Dose and Revaccination will include all vaccinated subjects from the ZOSTER-006/022 studies who received at least one additional dose of HZ/su vaccine in the ZOSTER-049 study.

The TVC for the Control group will include vaccinated subjects from the ZOSTER-006/022 studies who are enrolled and randomized in Control group of ZOSTER-049.

The TVC for immunogenicity and humoral/CMI persistence will include subjects for whom data related to immunogenicity and humoral/CMI persistence endpoints are available.

The TVC for analysis of safety will include:

- For 1-Additional Dose and Revaccination groups only, the TVC for the analysis of solicited symptoms will include all subjects who received at least 1 dose of the study treatment in ZOSTER-049 and who have documented solicited symptoms (i.e., diary card for solicited AEs completed and returned).
- For 1-Additional Dose and Revaccination groups, the TVC for the analysis of any other AEs other than solicited symptom will include all subjects who received at least 1 dose of the study treatment in ZOSTER-049.
- For Control and LTFU groups, the TVC for the analysis of any AEs will include all subjects who came for Month 0 visit.

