**CONFIDENTIAL**

201190 (ZOSTER-049 EXT:006-022)  
Protocol Amendment 5 Final

The primary analysis will be to assess the VE during this study and will use the historical control estimates adjusted for age at randomisation during the ZOSTER-006/022 studies. The method using the historical control estimates will be further explained in the Statistical Analysis Plan (SAP). Vaccine effects will be estimated by calculating the VE and estimating 95% CIs based on the variance of the observed population in this study and treating the historical control as constant.

The secondary analysis will be to assess the VE over each year of follow-up. Results from the ZOSTER-006/022 studies will be pooled for each year after vaccination with methods used in these studies. For overlapping years between ZOSTER-006/022 studies and this study, all the data will be pooled. For the non-overlapping years only the data from this ZOSTER-049 study will be used.

The assessment of the VE over the overall period including period from vaccination during the ZOSTER-006/022 studies up to the end of this long-term study will be done with a method that will be described in the SAP.

Any available information for the diagnosis of HZ episodes (clinical diagnosis, PCR, laboratory methods, etc.) during the interval between the end of the ZOSTER-006/022 studies and beginning of the ZOSTER-049 study is to be collected. Confirmation of all of these cases in the exact way as what will be done for cases collected during the clinical study follow-up periods of the ZOSTER-006, ZOSTER-022 and ZOSTER-049 will not be possible. Therefore, these cases will not be part of all efficacy analyses. A sensitivity analysis to assess the impact of these cases on the VE will be performed (this will be described in the SAP).

The purpose of these analyses will be descriptive and therefore the CIs will not be adjusted for multiple testing.

The analyses will be performed for confirmed HZ cases, for PHN and for complications (other than PHN).

Any exploratory or sensitivity analysis may be performed in addition to the analyses described above on an ad-hoc basis. However, the significance level of those analyses may not be fully controlled.

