## **5.2. *Modified Total Vaccinated cohort – (LTFU and Control group)***

The mTVC will be the primary population for efficacy analysis, which excludes subjects in the TVC for efficacy analysis who were not administered with the second vaccination during the ZOSTER-006/022 study, or who developed a confirmed case of HZ prior to 1 month after the second vaccination in the ZOSTER-006/022 primary study.

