**Table 1 Efficacy analyses per study periods and age-strata**

Analysis	Study period	≥ 50 YOA	≥ 60 YOA	≥ 70 YOA	50-59 YOA	60-69 YOA	70-79 YOA	≥ 80 YOA	Objective
A	Z-049 duration overall	X	X	X	X	X	X	X	Primary and Secondary
B	Z-006/Z022 * + Z049 duration overall	X	X	X	X	X	X	X	Secondary
C	Z-006/022 + Z-049 duration yearly**	X	X	X	X	X	X	X	Secondary and CCI

YOA = Year of age

\* from one month post dose 2 in the ZOSTER-006/022 studies

\*\* yearly follow-up will be computed from one month post dose 2 in the ZOSTER-006/022 studies. Note that results from the pooled ZOSTER-006/022 studies will be presented for each year after vaccination with methods used in these studies.

The primary analysis of efficacy will be performed on the mTVC, the analysis will be also performed on the TVC for efficacy and the ATP for efficacy to complement the mTVC analysis.

The **VE analysis for HZ** on TVC, mTVC and ATP cohort for efficacy over the study duration of present study ZOSTER-049 will be performed over the follow-up time calculated from enrolment in the present study to the time of first confirmed HZ case for a subject with a confirmed HZ case, and to the date of last contact for subjects without the occurrence of confirmed HZ case.

The **VE analysis for HZ** on mTVC and ATP cohort for efficacy over the duration starting from ZOSTER-006/ -022 study will be performed over the follow-up time calculated from one month post Dose 2 to the time of first confirmed HZ case for a subject with a confirmed HZ case, and to the date of last contact for subjects without the occurrence of confirmed HZ case.

The **VE analysis for HZ** on the TVC will be performed over the complete follow-up period and will include confirmed HZ cases from Dose 1 administered in the ZOSTER-006/022 studies for vaccine efficacy evaluation. The end of the follow-up period will be calculated according to the same principle as will be done for the mTVC and ATP analyses for efficacy, i.e., up to the confirmed HZ case for a subject with a confirmed HZ case, or up to the date of last contact for subjects without a confirmed HZ case.

***In the VE analysis for PHN and HZ related complication (other than PHN), the follow-up time will be calculated in the similar way as in VE analysis for HZ.***

All above analyses will be performed overall and by age strata. The age strata for VE are defined as: **50-59, 60-69, 70-79, ≥80, ≥60, ≥70 YOA** at primary vaccination in ZOSTER-006/022 studies.

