#### 6.2.2.2. **Sensitivity analysis including suspected HZ cases captured in the gap between primary studies and ZOSTER-049 study.**

*In the current calculation of VE for study ZOSTER-049, the suspected HZ cases during the time between the last visit of studies ZOSTER-006/022 and initiation of study ZOSTER-049 (the “gap period”) is not considered as confirmed cases. Per CHMP recommendation, a sensitivity analysis on the primary VE analysis during the entire follow-up period since ZOSTER-006/022 is planned to include potentially confirmed HZ cases during this gap period (Analysis B on mTVC-pooled ZOSTER-006/022 and mTVC-LTFU and Control group).*

*It is known that there are some self-reported suspected cases of HZ during the gap period, but these cases were not able to be confirmed as per the study protocol requirements, hence the true number of confirmed cases is unknown. The planned sensitivity analysis will assume different, yet conservatively high positive rates on the self-reported suspected cases to adequately assess the impact due to potentially confirmed cases. Please refer to Section 7.3.5 for more details*

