#### 6.2.2.3. **Sensitivity analysis considering subjects aging when enrolled into ZOSTER-049 from ZOSTER-006/022**

*Since all subjects enrolled in ZOSTER-049 study had aged for ~5 years compared to when they were enrolled in ZOSTER-006/022 studies, a sensitivity analysis on VE (analysis A, B and C on mTVC - LTFU and Control group only.) is planned to consider the aging factor on ZOSTER-049 subjects when utilizing the historical control to estimate the incident rate on the hypothetical control in ZOSTER-049 study. Please refer to Section 7.3.6 for more details*

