**If the follow-up period to be considered is from the primary study ZOSTER-006/022 study**

- *at the day after first vaccination (Month 0) if analyses are done on the Total Vaccinated Cohort for efficacy, or*
- *at 30 days after second vaccination (Month 3) if analyses are done on the mTVC or ATP cohort for efficacy.*

The follow-up time for each subject **will end:**

- at the time of the event; or,
- *at the time of receiving any vaccination for shingles which is not assigned as per protocol (for mTVC only); or,*
- at the latest visit for which data is available for subjects in case of no event. Practically, this will be set at the minimum date between the following dates
  - Date of withdrawal
  - Date of death *collected on the conclusion page for the subject who died*
  - Date of study conclusion
  - Cut off date for interim reporting for Y2, Y4

Start date of confirmed HZ case will be the earliest of the start date of the rash or start date of the pain to assess the onset of HZ, whichever comes first.

***Consideration on subjects who had HZ/PHN/HZ related complication (other than PHN) cases in ZOSTER-006/022 studies and were enrolled into ZOSTER-049 study:***

- *For the VE analysis in the prevention of HZ/PHN/HZ related complication (other than PHN) over the total duration of the ZOSTER-049 study, these subjects with previous confirmed cases will be excluded from ZOSTER-049 data.*

- *For the VE analysis in the prevention of HZ/PHN/HZ related complication (other than PHN) from one month post dose 2 in the ZOSTER-006/022 studies until the end of the ZOSTER-049 study, the first confirmed case will be considered, and the corresponding follow-up times will be censored to the time at 1st confirmed episode.*

*As there is no elimination code in primary studies ZOSTER-006/022 which eliminate subject with confirmed HZ episode, it will not be identified by elimination but rather by creating flag based on the w\_algo dataset generated during primary analysis.* The follow-up time will be calculated in days as Date of end of follow-up period – Date of vaccination +1 and expressed in person-years at risk (number of days/365.25).

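### The SAP gives incompatible populations for Analyses B and C: the efficacy cohorts it defines hold only ZOSTER-049 enrolees, follow-up starts in ZOSTER-006/022, and the pooled cohort that other sections point to is never defined

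*SAP*

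**What the plan says.** **Cohorts.** SAP 5.1 opens with "The Total Vaccinated cohort (TVC) will include all subjects from the ZOSTER-006/022 studies who are enrolled in the ZOSTER-049" and then narrows this for efficacy: "The TVC for efficacy will include all subjects in the LTFU and control groups for whom data related to efficacy endpoints are available". The mTVC in 5.2 is a subset, which "excludes subjects in the TVC for efficacy analysis who were not administered with the second vaccination during the ZOSTER-006/022 study" or who had confirmed HZ too early. The ATP efficacy cohort in 5.3 is headed for the same two groups. The elimination codes in 5.7 and Appendices 2 and 3 cover these cohorts and no pooled one.

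**Time zero.** For the period that begins in the primary studies, SAP 6.2.1 says the TVC analysis "will include confirmed HZ cases from Dose 1 administered in the ZOSTER-006/022 studies for vaccine efficacy evaluation". For the other two cohorts, SAP 7.3.1 starts the clock "at 30 days after second vaccination (Month 3) if analyses are done on the mTVC or ATP cohort for efficacy".

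**Comparator.** For Analysis B, SAP 7.3.3 uses the placebo rate observed in ZOSTER-006/022 for the primary period and the predicted rate for ZOSTER-049.

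**Text pointing to pooling.** On yearly efficacy, Protocol 11.7.2 says: "For overlapping years between ZOSTER-006/022 studies and this study, all the data will be pooled". The footnote to SAP Table 1 also promises yearly results from the pooled primary studies. SAP 6.2.2.2, on gap-period cases, names its population as "Analysis B on mTVC-pooled ZOSTER-006/022 and mTVC-LTFU and Control group".

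**Ageing sensitivity.** SAP 6.2.2.3 plans "analysis A, B and C on mTVC - LTFU and Control group only".

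**The concern.** Enrolment in ZOSTER-049 happens years after the clock starts for Analyses B and C. If the cohorts of section 5 are applied as written, a vaccinee's primary-study time counts only if that person was later alive, in contact, eligible and willing to return. Placebo time carries no such condition. HZ cases in vaccinees who did not return would vanish from the vaccine side together with their follow-up.

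The documents suggest a direction for one part of this. Protocol 5.3 bars people with immunosuppressive conditions or treatment, or with important underlying illness, and Protocol 1.1 says impaired cell-mediated immunity raises HZ risk. Applying those entry filters backwards would remove higher-risk people from the vaccine side only, which would tend to raise VE. Other reasons for returning or not could act either way.

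B and C serve secondary objectives. B also covers PHN and other complications, a forest plot, and the subgroups by gender, race, region and ethnicity. Two programmers could follow this SAP faithfully and report different estimates.

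**Working it through.** **1. Reproduce the plan's own figure (Protocol 11.4).**
- ZOSTER-006: 7344 in the mTVC, about 50% not returning: 7344 × 0.50 = 3672.
- ZOSTER-022: 13,500 vaccinated across both arms, 90% evaluable: 13,500 / 2 × 0.90 = 6075. With 55% not returning: 6075 × 0.45 = 2733.75, or 2734.
- Total: 3672 + 2734 = 6406, as stated.

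**2. Share kept if section 5 is applied literally.**
- Vaccine mTVC in the primary studies: 7344 + 6075 = 13,419.
- Kept: 6406 / 13,419 = 47.7%. Left out: 52.3%.
- With the rounded figure of about 6000 in Protocol 11.4.1: 6000 / 13,419 = 44.7% kept, 55.3% left out.

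**3. Person-years.** Mean primary follow-up was about four years (Protocol 1.2.1). I assume it is the same for returners and non-returners.
- All vaccinees: 13,419 × 4 = 53,676.
- Returners: 6406 × 4 = 25,624.
- Left out: 53,676 − 25,624 = 28,052, or 52.3%.

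**4. Share kept on the pooled reading.** All 13,419 contribute to the primary period, so the loss is 0%.

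**5. What selection could do to the primary-period estimate on the literal reading.** Let k be the probability that a vaccinee with primary-period HZ returns, divided by that for a vaccinee without. With rare events, apparent VE = 1 − (1 − VE) × k. The documents do not give k, so the values below are assumptions. The two VE levels are those in the titles of Protocol Tables 29 and 30.

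| k | True VE 80% | True VE 65% |
|---|---|---|
| 0.5 | 90% | 82.5% |
| 0.75 | 85% | 73.8% |
| 1 | 80% | 65% |
| 1.5 | 70% | 47.5% |

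**6. Ageing analysis, sections side by side.** SAP 6.2.2.2 lists the pooled primary mTVC and the LTFU and Control mTVC as two components. SAP 6.2.2.3 then uses the second label alone for A, B and C. SAP 7.3.3 says this analysis departs from the main one only in the age group to which the control rates are applied. If main Analysis B is pooled and the label in 6.2.2.3 means ZOSTER-049 enrolees, then population and control rate both change, contrary to 7.3.3.

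**The case against.** A reader of section 5 might infer that the vaccine side of B and C is in fact selected on returning and that half its early data are discarded. The documents do not support that as a statement of what will be done.

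- SAP 6.2.2.2 names a pooled population for Analysis B. SAP 7.3.5 computes that sensitivity result by the steps of Analysis B with updated cases and follow-up, so it is evidence of how B itself is run.
- Protocol 11.7.2 and the Table 1 footnote pool primary-study data for the yearly analysis.
- SAP 7.3.1 subtracts the gap for subjects who came back, a qualification that would be idle if everyone analysed had come back.
- No efficacy text expressly limits early person-time to returners.

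On the ageing analysis, the last word of 6.2.2.3 may mean only that the TVC and ATP versions are not run. That would agree with 7.3.3. Confounding of ageing with population is therefore possible but not established.

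These points stand for the mTVC in B and for C. They do not close the matter. The pooled cohort appears only in a parenthesis within a sensitivity analysis. Nothing comparable is named for the TVC or ATP versions. SAP 6.2.1 also says C is planned similarly to A, which covers enrolees. The cohort definitions that are formally stated still point the other way.

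**Conclusion.** The SAP contradicts itself on who contributes primary-period vaccine follow-up to Analyses B and C. The only efficacy cohorts it defines would condition that follow-up on a later event, while the comparator is unselected. The text that describes the analyses points to full pooling.

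The 52% (about 28,000 of 53,700 person-years) measures the distance between the two readings. It is not an established loss. It rests on planned return rates, equal mean follow-up and a literal reading of section 5; on the pooled reading it is zero. The bias figures depend on an assumed k and show sensitivity only.

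For TVC and ATP in B and C, no text names a pooled population at all. For the ageing versions of B and C, 6.2.2.3 and 7.3.3 need to be reconciled before any shift can be put down to ageing.

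Primary Analysis A starts at ZOSTER-049 enrolment and does not have this problem. B and C are secondary and descriptive, with no success criteria. The SAP should be corrected, but the primary result is not in doubt on this account.

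**What to change.** - In SAP 5.1 to 5.3, 5.7 and 6.2.1, state that the ZOSTER-049 efficacy cohorts apply to Analysis A.
- For Analyses B and C, define pooled TVC, mTVC and ATP cohorts: all HZ/su and placebo recipients in the corresponding ZOSTER-006/022 cohort. Non-returners contribute until the end of primary-study follow-up.
- Add ZOSTER-049 follow-up only for re-enrolled subjects in the LTFU and Control groups. Subjects in the 1-Additional Dose and Revaccination groups contribute primary-study time only, since the efficacy cohorts leave out their ZOSTER-049 time.
- In 6.2.2.3, run the ageing versions of B and C on the same pooled mTVC, changing only the control rate for the ZOSTER-049 part.

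The cost is SAP wording and matching elimination rules. The pooled ZOSTER-006/022 data are already in use, so no new data are needed.
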